### **3. Selection of Study Population**

#### **3.1 Inclusion Criteria**

Only subjects who met all of the following conditions were included in this study:

- 1) Patients must be able to understand and sign the informed consent form (ICF), and be able to comply with all study procedures.
- 2) Male or female patients over 40 years old who planned to undergo phacoemulsification combined with intraocular lens implantation surgery.

#### **3.2 Exclusion Criteria**

Subjects were not allowed to participate in this study if they met any of the following criteria:

- 1) Known allergy to dexamethasone or any component of the Dexamethasone Insert.
- 2) History of endophthalmitis of any cause in either eye, presence of corneal abnormalities or malnutrition.
- 3) Patients with ocular hypertension, with an IOP >21 mmHg in the study eye at screening, regardless of anti-glaucoma monotherapy.
- 4) Posterior capsule rupture or lens dislocation, anterior hyaloid membrane rupture, vitreous loss, and floppy iris syndrome during cataract surgery.
- 5) Other circumstances that, in the opinion of the investigator, the subject was not suitable for participation in the study.

### **4. Statistical Plan**

Descriptive statistics will be performed for de-identified demographic data, surgical details, clinical outcomes, and surgeon satisfaction.

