## Study Summary

Title	A Real-world Study on the Efficacy and Safety of 9% Dexamethasone Insert in the Treatment of Postoperative Inflammation Following Cataract Surgery
Protocol Number	OT-502-002
Study Phase	Real-word Study
Study Duration	90 days
Study Center(s)	2 sites
Objectives	To evaluate the efficacy and safety of Dexamethasone Insert in the treatment of postoperative inflammation following cataract surgery in real-world clinical settings; and to evaluate the ease of use, time taken, and safety of the Dexamethasone Insert injector
Numbers of subjects	Plan: 263 subjects (113 subjects in the 9% Dexamethasone Insert group, 150 subjects in the external control group). Actual enrollment: 113 subjects in the 9% Dexamethasone Insert group, 150 subjects in the external control group; after propensity score (PS) 1:1 matching, 208 subjects (104 subjects in the 9% Dexamethasone Insert group, 104 subjects in the external control group) were included in the post-matching analysis.
Eligibility Criteria	
Inclusion Criteria:
 
 
1) Patients must be able to understand and sign the informed consent form (ICF), and be able to comply with all study procedures.
 
2) Male or female patients over 40 years old who planned to undergo phacoemulsification combined with intraocular lens implantation surgery.
 
 
Exclusion Criteria:
 
 
1) Known allergy to dexamethasone or any component of the Dexamethasone Insert.
 
2) History of endophthalmitis of any cause in either eye, presence of corneal abnormalities or malnutrition.
 
3) Patients with ocular hypertension, with an intraocular pressure (IOP) >21 mmHg in the study eye at screening, regardless of anti-glaucoma monotherapy.
 
4) Posterior capsule rupture or lens dislocation, anterior hyaloid membrane rupture, vitreous loss, and floppy iris syndrome during cataract surgery.
 
5) Other circumstances that, in the opinion of the investigator, the subject was not suitable for participation in the study
 

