## 2. Overall Study Design and Plan

This was a prospective, real-world study. It was planned to prospectively collect the medical histories and follow-up data of 113 subjects who received Dexamethasone Insert in real-world settings in China, to evaluate the efficacy and safety of Dexamethasone Insert, and conduct a survey among 30 injector users on the ease of use, time taken, and safety of using the Dexamethasone Insert injector. Prospectively enrolled subjects returned to the study sites in Hainan for follow-up on Days 1, 8, 30, and 90 after Dexamethasone Insert injection. In addition to prospectively collecting data from subjects receiving Dexamethasone Insert as mentioned above, data from 150 cataract subjects previously treated using conventional clinical methods at selected medical institutions were also prospectively collected as an external control (conventional treatment) to further evaluate the efficacy and safety of the Dexamethasone Insert. Prospective collection of data of the external control subjects was conducted as consistently as possible with that of the Dexamethasone Insert group.

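### Section 4 plans only descriptive statistics for clinical outcomes, so the matched 104 versus 104 comparison with the external control has no stated effect measure or confidence interval

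*Combined protocol and SAP*

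**What the plan says.** Section 4 (Statistical Plan) consists of one sentence: "Descriptive statistics will be performed for de-identified demographic data, surgical details, clinical outcomes, and surgeon satisfaction". It names no between-group contrast, interval, test or model, and it does not mention matching. Nothing in the section is marked as redacted.

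The design sections describe a comparison group. Under Section 2 (Overall Study Design and Plan), "data from 150 cataract subjects previously treated using conventional clinical methods at selected medical institutions were also prospectively collected", and they serve "as an external control (conventional treatment) to further evaluate the efficacy and safety of the Dexamethasone Insert". The same section adds: "Prospective collection of data of the external control subjects was conducted as consistently as possible with that of the Dexamethasone Insert group".

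The Study Summary, under numbers of subjects, gives 113 insert and 150 external control subjects, both planned and enrolled. It then reports that, after 1:1 propensity score matching, "208 subjects (104 subjects in the 9% Dexamethasone Insert group, 104 subjects in the external control group) were included in the post-matching analysis".

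**The concern.** The stated method and the design do not meet. Summaries by group are adequate for describing the insert cohort, the surgical details and the answers of the injector users. One-to-one propensity score matching has a different purpose: it gives up subjects to make two groups comparable, and the quantity of interest is then the difference between them. Section 4 stops short of that quantity and of its precision.

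Two misreadings follow if only group summaries are reported. A chance difference between 104 and 104 subjects can be taken as a benefit of the insert. Similarly low event counts in the two groups can be taken as evidence of similar safety. An interval for the difference shows how far sampling error alone could make either reading wrong. Because the plan is silent, the choice of effect measure, of interval method and of how to treat the pairing is also left open until the data are in hand.

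The point is limited. The documents state no hypothesis, so what is missing is an estimate with its precision, not a significance test.

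**Working it through.** **Inputs from the documents.** 113 insert and 150 control subjects before matching, 104 and 104 after (Study Summary); descriptive statistics only (Section 4). The plan has no power, precision or sample-size figure to reproduce. The counts agree: 113 + 150 = 263 and 104 + 104 = 208. Matching left out 113 − 104 = 9 insert and 150 − 104 = 46 control subjects.

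**Assumptions.** The documents give no outcome rates, event counts, SDs or confidence level. All rates and counts below are therefore illustrative, with two-sided 95% intervals. The groups are first treated as independent; pairing is taken up in step 4.

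**1. Binary outcomes at moderate rates.** With a common rate p, the half-width for a risk difference is 1.96 × √(2p(1−p)/104).

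| Assumed p | Half-width (percentage points) |
|---|---|
| 50% | ±13.6 |
| 30% or 70% | ±12.5 |
| 20% or 80% | ±10.9 |
| 10% or 90% | ±8.2 |

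**2. Continuous outcomes.** In SD units, the half-width for a mean difference is 1.96 × √(2/104) = ±0.27 SD.

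**3. Sparse events and unequal results.** Here the Newcombe interval is used. It combines the Wilson limits (l, u) of the two proportions: lower limit = d − √((p₁−l₁)² + (u₂−p₂)²), upper limit = d + √((u₁−p₁)² + (p₂−l₂)²).

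| Insert | Control | Difference (points) | 95% interval (points) |
|---|---|---|---|
| 5/104 | 5/104 | 0 | ±6.6 |
| 2/104 | 2/104 | 0 | ±5.0 |
| 0/104 | 0/104 | 0 | ±3.6 |
| 85/104 | 73/104 | 11.5 | −0.1 to 22.8 |
| 86/104 | 73/104 | 12.5 | 0.9 to 23.7 |

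For 0/104 the Wilson upper limit is 1.96²/(104 + 1.96²) = 3.84/107.84 = 3.6%, which is also the half-width for the difference. For 86/104 (82.7%; Wilson 74.3% to 88.8%) against 73/104 (70.2%; Wilson 60.8% to 78.1%), the lower limit is 0.125 − √((0.8269−0.7429)² + (0.7814−0.7019)²) = 0.009.

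So no events in either group still leaves a difference of up to about 3.6 points either way. With 70.2% in the control group, an apparent gain of 11.5 points still has an interval that reaches just below zero.

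**4. Effect of pairing.** A within-pair correlation r multiplies the half-width by √(1−r). At p = 50%, an assumed r of 0.1 gives 13.6 × √0.9 = ±12.9 points, and r of 0.3 gives 13.6 × √0.7 = ±11.4 points. Pairing narrows the interval somewhat but leaves it wide.

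**The case against.** The strongest defence is that the plan is consistent with its own aims. The stated objective is "To evaluate the efficacy and safety of Dexamethasone Insert in the treatment of postoperative inflammation following cataract surgery in real-world clinical settings", together with an assessment of the injector, and it names no comparison with control. There is no hypothesis, margin or sample-size claim. A descriptive analysis is a legitimate choice for a small real-world study, and descriptive statistics can include a difference with an interval. Harm arises only if the report stops at group summaries. The matching was done although Section 4 never mentions it, so the actual analysis may have gone further still.

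It can also be said that sampling error is not the main threat. The control subjects were treated earlier, at selected institutions, so bias from site, period and unmeasured differences may be larger, and a narrow interval could reassure falsely. The documents name no endpoint, comparison visit, matching covariates, caliper or balance criterion. Without an endpoint, a risk or mean difference has nothing definite to attach to. With visits on Days 1, 8, 30 and 90, intervals for every outcome would be numerous. Finally, enrolment and matching are already complete.

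Much of this stands as a limit on the point. The harm is conditional, every rate above is assumed, the endpoint and matching details are further gaps, and a change now may have to be called post hoc. None of it supplies what is missing. A 1:1 match and a post-matching analysis imply a comparison, and no section says how that comparison is to be expressed or how precise it is.

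**Conclusion.** The concern holds and should be fixed. Followed exactly, Section 4 yields side-by-side summaries with no measure of uncertainty for the comparison that the matched sample was built to support. At assumed rates of 10% to 90%, the unreported uncertainty is about ±8 to ±14 percentage points for a risk difference with independent groups. It is ±0.27 SD for a mean difference, and about ±4 to ±7 points for zero to five events per group. Moderate within-pair correlation changes these figures little.

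The omission itself rests on the text and needs no assumption; only its size does. It is not a critical defect, because no hypothesis is stated and the external control is described as a further source of evidence. Confidence is high.

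**What to change.** Keep descriptive statistics in Section 4 for demographics, surgical details and the injector survey, and add wording along these lines:

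> Clinical efficacy and safety outcomes will be compared between the insert and external control groups in the 1:1 matched sample as risk differences (binary) or mean differences (continuous), with 95% confidence intervals that account for the matched pairs. Score-type or exact intervals will be used for sparse events. The comparison is exploratory. The intervals reflect sampling error only, not bias from site, period or unmeasured differences.

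List the outcomes and visits to which this applies, since the documents name none for the comparison. Date the change, and label it post hoc if outcomes had already been seen, because the Study Summary shows that enrolment and matching were complete.

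The cost is a short text change and modest extra analysis of data already collected, with no new subjects. There are three downsides: the intervals may show the comparison to be imprecise, the post hoc label may be needed, and a narrow interval could mislead if the statement about sampling error is left out.

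### No planned step adjusts the 104 v 104 matched outcomes for demographics, screening IOP or surgical details, so ordinary differences in surgical trauma could be read as an Insert effect.

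*Combined protocol and SAP*

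**What the plan says.** The whole of Section 4 (Statistical Plan) is one sentence: "Descriptive statistics will be performed for de-identified demographic data, surgical details, clinical outcomes, and surgeon satisfaction". It gives no between-group estimate, outcome model, covariate adjustment or confidence interval.

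Elsewhere the study is comparative. Section 2 (Overall Study Design and Plan) says that "data from 150 cataract subjects previously treated using conventional clinical methods at selected medical institutions were also prospectively collected as an external control", with the aim "to further evaluate the efficacy and safety of the Dexamethasone Insert". The Study Summary gives the planned numbers as "Plan: 263 subjects (113 subjects in the 9% Dexamethasone Insert group, 150 subjects in the external control group" and then reports the analysis set: "after propensity score (PS) 1:1 matching, 208 subjects (104 subjects in the 9% Dexamethasone Insert group, 104 subjects in the external control group". It does not say which covariates entered the score, what caliper was used or how balance was judged.

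Two exclusions in Section 3.2 bear on the point. Criterion 3 excludes ocular hypertension "with an IOP >21 mmHg in the study eye at screening", so IOP is measured before surgery, at least in the Insert group. Criterion 4 excludes "Posterior capsule rupture or lens dislocation, anterior hyaloid membrane rupture, vitreous loss, and floppy iris syndrome during cataract surgery".

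**The concern.** The outcome of interest is inflammation caused by an operation, so how the operation went bears directly on it. Screening IOP is likewise the natural baseline for any IOP outcome. Insert subjects were followed in Hainan, while controls had been treated earlier at selected institutions. Surgeon, technique and period may therefore differ between the groups.

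One-to-one matching balances variables in the score only approximately, and it does not directly balance those left out. As the score is not described, a reader cannot tell which of the two applies to surgical details. If trauma differs between the matched groups and nothing adjusts for it, the difference appears in the outcome contrast as if the Insert had caused it. Separately, a contrast that ignores prognostic variables already on file is usually less precise than it could be.

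**Working it through.** **Inputs from the documents.** 113 + 150 = 263 planned and 104 + 104 = 208 matched, so both sums hold. Matching dropped 113 − 104 = 9 Insert subjects and 150 − 104 = 46 controls. The documents give no alpha, power, outcome rate, SD, effect size or covariate–outcome association, so neither 263 nor 208 can be derived from a formula. Every further input below is an assumption.

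**Bias on the risk-difference scale.** Assume an outcome rate near 50%, a residual standardised difference d in one surgical variable, and an odds ratio of 1.5 to 2 per SD of that variable. With L = d × ln(OR), the spurious risk difference is expit(L/2) − expit(−L/2).

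| d (SD) | OR 1.5 | OR 2 |
|---|---|---|
| 0.1 | 1.0 points | 1.7 points |
| 0.2 | 2.0 | 3.5 |
| 0.3 | 3.0 | 5.2 |
| 0.5 | 5.1 | 8.6 |

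For example, d = 0.2 and OR 2 give L = 0.2 × 0.693 = 0.139 and a shift of 3.5 points.

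**The same check for a continuous outcome, in SD units.** SE = √(2/104) = 0.139. Bias = d × slope, where the slope is the assumed covariate–outcome association in SD units. The type I error is for a nominal two-sided 5% test, also an assumption.

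| d | slope | bias (SD) | type I error |
|---|---|---|---|
| 0.1 | 0.3 | 0.03 | 5.5% |
| 0.2 | 0.3 | 0.06 | 7.2% |
| 0.3 | 0.5 | 0.15 | 19% |
| 0.5 | 0.5 | 0.25 | 44% |

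The range runs from negligible to serious, and nothing in the documents locates the trial within it.

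**Precision.** At a 50% rate, treating the groups as independent, the 95% half-width is 1.96 × √(2 × 0.25/104) = 13.6 points. If covariates explain a share R² of outcome variance, the SE is multiplied by about √(1 − R²).

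| R² | SE reduction | half-width |
|---|---|---|
| 0.10 | 5% | 12.9 points |
| 0.20 | 11% | 12.2 |
| 0.30 | 16% | 11.4 |

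These gains are upper figures for each R², because an analysis that uses the pairing may already capture part of them.

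**The case against.** The strongest reply is that 104 v 104 is itself the product of adjustment. A propensity score needs covariates, and demographics or surgical details may well be among them. A reader might infer from Section 4 that these variables are merely tabulated and play no part in the comparison. The documents do not support that: they are silent on what went into the score. What stands is that the covariates are unnamed and that no adjustment after matching is stated.

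Second, criterion 4 in Section 3.2 removes the major intraoperative complications, and entry is limited to planned phacoemulsification with lens implantation. This makes the larger imbalances less plausible, and nothing in the documents supports 0.5 SD in particular. Variation among uncomplicated operations remains.

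Third, adjustment presupposes a defined contrast, and Section 4 names no primary endpoint. The added model can therefore apply only to those outcomes that are in fact compared between groups. It is also unverified that screening IOP and comparable surgical details exist for the controls, since Section 2 promises only that their data collection was kept as similar as was feasible.

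Fourth, a reader might suspect that total operating time, which could include the injection step, sits in the score and should be taken out. No section mentions operating time as a collected variable; the only time recorded concerns use of the injector. Removing a score variable would also mean rematching. The general rule against adjusting for anything the injection can affect is sound, but the documents give no ground for changing the match.

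**Conclusion.** The concern holds in a limited form. The plan sets up a non-randomised matched comparison, leaves the score's covariates unnamed and states no step that adjusts the matched outcomes for demographics, screening IOP or surgical details. Ordinary differences in surgical trauma can therefore remain in the contrast.

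The size is not known. The 1 to 9 points depend on assumed imbalances of 0.1 to 0.5 SD, assumed odds ratios of 1.5 to 2 per SD and a rate near 50%. The 5% to 16% smaller standard error depends on an assumed R² of 0.10 to 0.30 and on independent groups. It would be near zero if the covariates predict little. A reader should not conclude that the comparison is shown to be biased; the documents show only that bias of this kind is neither ruled out nor addressed. Adjustment would not remove unmeasured differences between surgeons or sites.

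This is a change that should be made, at medium confidence. Because the Study Summary already reports the completed match, any analysis added now is post hoc.

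**What to change.** Leave the existing match unchanged and add the following to Section 4:

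1. List the covariates used in the propensity score, and report post-match standardised differences for them and for the surgical details fixed before the Insert is injected.
2. For each clinical outcome compared between groups, fit a regression in the 104 pairs on group plus age, sex, screening IOP and pre-injection surgical details, where these are recorded in both groups.
3. Report the standardised risk or mean difference with a pair-clustered 95% confidence interval beside the unadjusted matched figure.
4. Label the adjusted result as a post hoc sensitivity analysis.
5. Do not adjust for any variable that the injection itself can affect.

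The cost is one balance table, one extra model per compared outcome, and a simple stated rule for covariates missing in the controls. No new data are needed where the variables are already recorded in both groups; where they are not, the report should say so.
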